## Background

According to World Health Organization (WHO), in 2010, Polycystic Ovarian Syndrome (PCOS) affected approximately 116 million women worldwide (3.4% of the population). This condition caused symptoms in about 5-10% of women of reproductive age (12 – 45 years). It has been considered one of the most common causes of female infertility and the most common endocrine disorder (Boomsma, Fauser, and Macklon 2008; Teede, Deeks, and Moran 2010). The standard diagnosis for the syndrome dates back to international conferences organized by the National Institutes of Health (NIH) in 1990 (Zawadzki and Dunaif 1992) and the Rotterdam European Society of Human Reproduction and Embryology/ American Society for Reproductive Medicine (ESHRE/ASRM) sponsored PCOS consensus workshop group in 2003 and 2004 (Rotterdam ESHRE/ASRM-sponsored PCOS consensus workshop group 2004). Clinical manifestations of the disease may include menstrual irregularities, amenorrhea, ovulation-related infertility, polycystic ovaries, and signs of androgen excess such as acne and hirsutism. This condition may also lead to chronic diseases such as obesity, type 2 diabetes (T2D), dyslipidaemia, and cardiovascular events (Palomba et al. 2015; Mohammed and Nayak 2017).

## Statement of Problem

Despite the increasing knowledge concerning PCOS, the global picture of the disorder is deficient in a number of geographic regions. Understanding the global prevalence and phenotypic presentation of any common disorder, including PCOS, allows for:

1. A determination of the prevalence and associated morbidities of the disorder, to better assess the public health and economic implications of PCOS in this region.
2. A determination of the phenotype of PCOS in this region, allowing for improved screening methods.
3. The elucidation of underlying environmental or ethnic factors that may affect the prevalence, severity or complications of the disorder, via comparison of data between countries.

4. The elucidation of genetic variants underlying the disorder in this region, fostering and improved understanding of the molecular mechanisms underlying the disorder and a better understanding of the evolutionary selection processes that have paradoxically resulted in the current high prevalence of the disorder in the face of obvious reproductive deficits.

#### Benefit

These data would not only lead to improved understanding of the public health implications of the disorder in Trinidad, but also potentially highlighting novel etiologic avenues and therapeutic targets.

#### Aims and objectives

##### Primary:

1. To determine the prevalence of PCOS among women of reproductive age (a selected population (18 to 45)) in Trinidad.

##### Secondary

2. To determine the distribution of phenotypes among women diagnosed with PCOS in the above objective overall and by ethnicity. PCOS sub phenotypes are as follows: Phenotype A – clinical and/or biochemical hyperandrogenism (HA) and oligi-/anovulation (OA), and polycystic ovarian morphology (PCOM); B – HA and OA; C – HA and PCOM; and D – OA and PCOM;
3. To determine the risks for, metabolic syndrome, depression, obstructive sleep apnea symptoms, fibroids, and general health issues for PCOS women versus women without PCOS in the age groups 18 – 45 years.
4. To determine the genotype of PCOS in Trinidad.

#### Outcome measures and variables

##### Outcome measures (dependent variables)

5. Primary outcome
  - ii) Prevalence of PCOS and its symptoms
6. Secondary outcome
  - iv) Phenotype of PCOS
  - v) Genotype of PCOS
  - vi) Prevalence and prevalence ration for PCOS subphenotypes in Trinidad, odds ratio for metabolic syndrome, depression, obstructive sleep apnea symptoms, fibroids, and general patient health issues, adjusted for age, ethnicity, BMI, treatment (OCP), and socioeconomic parameters.

##### Covariates (independent variables)

- a) Socio-demographic variables

## b) Baseline characteristics

### Methodology

#### Study design

This is a prospective, cross sectional study. The study will be conducted among females in Trinidad from different geographical locations.

#### Study period

The study will be conducted over a one-year period, from 1st January 2023 to 31st June 2024.

#### Study sites

The study will be conducted at The Faculty of Medical Sciences.

#### Study population

Based on a review of nine studies conducted in the general population, a conservative prevalence estimate for PCOS, using the Rotterdam 2003 definition, is 13.4%. Based on this formula, a sample size of 495 untreated individuals will be required to determine the prevalence with an absolute error of  $\pm 3\%$ . Assuming a 50% enrollment rate, 990 women would need to be approached for study inclusion. The study population will be females of reproductive age from Trinidad.

#### Strategies for Sampling, Recruitment and Retention

Participants will be sampled proportionally from all 8 zones as shown above in Trinidad. Approximately 124 women in the reproductive age (18 – 45 years old) will be randomly sampled from each zone. Houses will be numbered and random numbers of these houses will be generated using random number calculator. In each sampled house, females would be prescreened and those that satisfy our inclusion criteria would be selected. Telephone numbers of participants will be obtained and follow-up calls made.

Sample size calculations were based on the following formula (32):

$$n = [(Z_{1-\alpha})^2(P(1 - P)/D^2)]$$

where n = individual sample size,  $Z_{1-\alpha} = 1.96$  (when  $\alpha = 0.05$ ), P = assumed prevalence, and D = absolute error.

Sampling units are defined as individual unselected women between the ages of 18 and 45 years, identified in the community. We target power analysis on women who do not use hormonal contraception. We assume a conservative response rate of 50% of sampled women. This response rate includes the following parameters:

use of hormone/contraceptive use (15%), excluded due to hysterectomy or ovariectomy (3%), excluded due to pregnancy (2%), refusal to participate (20%), and study drop-out/lost to follow-up (10%).

A conservative prevalence estimate for PCOS based on a review of nine studies conducted in the general population using the Rotterdam 2003 definition is 13.4% (4, 5, 33-39). Using the above formula, a sample size of 495 individuals will be required to determine the prevalence with an absolute error of  $\pm 3\%$ . Assuming a 50% enrollment rate, 990 women would need to be approached for study inclusion.

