**Data management and Statistical analysis:**

Data entry, data processing, and statistical analysis will be done using IBM Statistical

Software for Social Sciences (SPSS, Inc., Chicago, IL) version 20.0. Continuous variables (such as age, anthropometric measurements, laboratory values of assay) will be checked for normality using one-sample

Kolmogorov-Smirnoff test, and expressed as means  $\pm$  standard deviation or median  $\pm$  interquartile range (for data that are not normally distributed).

Categorical variables (such as race, socioeconomic characteristics) will be expressed as frequencies with accompanying percentages. Differences between groups will be compared using the Pearson's Chi-square test or Fisher's exact test for categorical variables. Odds ratio and the corresponding 95% confidence intervals (CI) will be presented. The student t test and ANOVA will be used to compare difference between groups for normally distributed continuous variables. Comparison of continuous variables that were not normally distributed will be done using non-parametric (Mann-Whitney U test or Kruskal-Wallis test) inferential statistical test.

Linear and logistic regression analysis (univariate and multivariate) will be performed to evaluate the relationship between dependent and independent variables. Test of statistical significance will be set at p-value less than 0.05.

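### Houses are drawn at random and every qualifying woman in each is taken, but the ±3% precision and the analysis treat women as independent; the loss is probably modest, and household clustering should be recorded and allowed for.

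*Combined protocol and SAP*

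**What the plan says.** Under *Strategies for Sampling, Recruitment and Retention* the random draw is of houses: "Houses will be numbered and random numbers of these houses will be generated using random number calculator". Selection within a house follows: "In each sampled house, females would be prescreened and those that satisfy our inclusion criteria would be selected". There is no limit of one woman per house and no random draw within it. All eight zones are included, with about 124 women from each.

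The same section then describes a different unit: "Sampling units are defined as individual unselected women between the ages of 18 and 45 years, identified in the community". The sample size rests on a single-proportion formula whose only inputs besides the normal quantile are given as "P = assumed prevalence, and D = absolute error". There is no design-effect term. The inputs and result are: "A conservative prevalence estimate for PCOS based on a review of nine studies conducted in the general population using the Rotterdam 2003 definition is 13.4" per cent; "a sample size of 495 individuals will be required to determine the prevalence with an absolute error of" ±3%; and "Assuming a 50% enrollment rate, 990 women would need to be approached for study inclusion".

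*Data management and Statistical analysis* plans the comparisons as follows: "Differences between groups will be compared using the Pearson's Chi-square test or Fisher's exact test for categorical variables". It adds t tests, ANOVA, rank tests, and linear and logistic regression, and it promises 95% intervals for odds ratios. It mentions no household clustering, survey weights, GEE, mixed model or robust variance, and it names no interval method for the prevalence.

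*Sampling technique* states that recruitment in every phase is consecutive and does not mention the house draw.

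**The concern.** Women who live in one house may be related and often share ethnicity and surroundings. The *Statement of Problem* names environmental, ethnic and genetic factors as possible influences on PCOS, so some positive correlation between housemates is plausible. A house that supplies two or three women then carries less information on prevalence than the same number of women from separate houses.

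The primary result is a prevalence with a stated precision. If clustering is ignored, the ±3% and a simple binomial interval claim more than the design delivers. The same applies to the phenotype distribution by ethnicity, because ethnicity varies mainly between houses. If the household link is not kept in the data, the analyst can neither correct for clustering nor see how much there was.

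**Working it through.** **1. The plan's own figure.** With z = 1.96, P = 0.134 and D = 0.03:

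n = 1.96² × 0.134 × 0.866 / 0.03² = 495.3, which matches the stated 495.

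At n = 495 the half-width under independence is 1.96 × √(0.134 × 0.866 / 495) = 3.00%. The listed losses are 15 + 3 + 2 + 20 + 10 = 50%, and 495 / 0.50 = 990. The arithmetic is correct; the question is whether the independence formula fits the design.

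**2. Inputs the documents do not give (assumptions).**
- Eligible women per house: three illustrative mixes of houses with 1, 2, 3 or 4 such women, namely 80/16/4/0%, 65/25/8/2% and 50/30/15/5%.
- Within-house correlation ρ: 0.1, 0.3 and 0.5.

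**3. Retention from eligible to analysed.** The 495 are those left after losses, so the cluster size that matters is that of analysed women. If contraceptive use, surgery and pregnancy (15 + 3 + 2 = 20 points) are already removed from the eligible count, retention is 50 / 80 = 62.5%. It is assumed to be independent between women in a house.

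**4. Formulas.** Because house sizes differ, the design effect uses the woman-weighted size w = Σm² / Σm:
- after retention, w′ = 1 + 0.625 × (w − 1)
- DE = 1 + (w′ − 1) × ρ
- half-width = 3.00% × √DE
- effective n = 495 / DE
- coverage of a nominal 95% interval = 2Φ(1.96 / √DE) − 1

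**5. Results.**

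| Case | Mean m | w | w′ | ρ | DE | Half-width | Effective n | Coverage |
|---|---|---|---|---|---|---|---|---|
| One woman per house | 1.00 | 1.00 | 1.00 | any | 1.00 | ±3.00% | 495 | 95% |
| Low | 1.24 | 1.80/1.24 = 1.45 | 1.28 | 0.1 | 1.03 | ±3.04% | 481 | 94.7% |
| Middle | 1.47 | 2.69/1.47 = 1.83 | 1.52 | 0.3 | 1.16 | ±3.22% | 428 | 93.2% |
| High | 1.75 | 3.85/1.75 = 2.20 | 1.75 | 0.5 | 1.38 | ±3.52% | 360 | 90.5% |

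If all 50 points of loss fell on eligible women, the middle case would have w′ = 1 + 0.5 × 0.83 = 1.41, DE = 1.12 and a half-width of ±3.18%.

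**6. What the correlations imply.** At P = 13.4%, a housemate of a woman with PCOS has PCOS with probability 0.134 + ρ × 0.866. This is 22% at ρ = 0.1, 39% at 0.3 and 57% at 0.5. The high case is therefore demanding.

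**7. One woman per house as an alternative.** Choosing one woman at random and weighting by the number eligible costs a factor of E[m²] / E[m]²:
- 1.80 / 1.24² = 1.17
- 2.69 / 1.47² = 1.24
- 3.85 / 1.75² = 1.26

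Over the nine combinations of mix and ρ, this exceeds the clustering DE in seven. In one the two are nearly equal (1.24 against 1.26), and only in the high case is clustering clearly worse (1.26 against 1.38).

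**The case against.** The strongest reply is that the effect may be negligible. The *Inclusion criteria* require a symptom or sign, and half of those approached are expected to be lost; both push analysed women per house towards one, where the effect vanishes. The documents give no household composition and no correlation, and nothing in them supports a correlation as high as 0.5. All of this stands, and it is why the size is given as an assumed range that starts at zero. It does not remove the mismatch between the design and the formula.

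A reader might infer that every confidence interval in the study is too narrow. The documents do not support that. The only intervals promised are for odds ratios. In PCOS versus non-PCOS comparisons, a case and a non-case in one house can make the ordinary standard error too large, so the direction is not fixed. The claim of too narrow applies to a simple prevalence interval and to contrasts between houses such as ethnicity.

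A reader might also put the high-case house sizes straight onto the 495 and reach ±3.8% with 88% coverage (w = 2.20, ρ = 0.5, DE = 1.60). That ignores the losses the plan itself subtracts before reaching 495.

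Three further points stand. The consecutive sampling under *Sampling technique* conflicts with the house draw, so the design must be settled first. Zones are strata and may recover some precision if analysed as such. The register and data forms are cited as attachments that are not shown, so one cannot conclude that a household field is absent. The fields listed for the register under *Study procedure*, and the CRF sections described under data collection, simply do not mention one.

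Finally, admitting only women with symptoms is a separate and larger question for the prevalence estimate. It does not settle this one.

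**Conclusion.** The point holds in a limited form. The plan draws houses, takes all qualifying women in them, and then sizes and analyses the study as if individual women had been drawn independently. The 495 and 990 are arithmetically right, but ±3% is the value for a simple random sample.

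Under the stated assumptions the design effect is about 1.03 to 1.38 and the half-width ±3.04% to ±3.52%. The middle case is ±3.22%, with coverage of about 93% for a nominal 95% interval. There is no loss if each house yields one analysed woman. The direction is towards over-precision for prevalence and for ethnic contrasts where housemates share ethnicity, given positive correlation. It is undetermined for PCOS versus non-PCOS comparisons. House size and correlation are assumptions; that the design and the analysis do not match is in the text.

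This is worth correcting because it is cheap now and may be impossible later if the household link is lost. It does not invalidate the study.

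**What to change.** 1. Reconcile the house draw in *Strategies for Sampling, Recruitment and Retention* with the consecutive recruitment in *Sampling technique*, and state which design will be run.
2. Make sure a household ID is recorded for each woman and carried into the analysis database beside her individual ID.
3. Estimate prevalence with house as cluster and zone as stratum, and name the interval method. Use house-clustered standard errors (for example GEE or Complex Samples procedures in SPSS) for the regressions and group comparisons.
4. State that houses are the primary sampling units and that ±3% is the simple-random-sample value, with the assumed design-effect range beside it.

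The cost is one data field if it is not already on the forms, slightly more analysis work and a slightly less favourable stated precision. No extra women are needed, but these steps report the precision honestly and do not restore ±3%. Moving to one randomly chosen woman per house is not recommended: its weighting loss of about 1.17 to 1.26 is similar to or larger than the clustering loss in most of the assumed cases.

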## Selection criteria

### Inclusion criteria

- a) Female, ages 18 to 45 years., all ethnic backgrounds.
- b) The participants must have at least one of the following two features:
  - i) Dermatological signs or complains of clinical hyperandrogenism such as unwanted facial or body hair, loss of scalp hair (alopecia) or persistence acne (pimple).
  - ii) Signs or complains of ovulatory dysfunction such as irregular menses (oligomenorrhoea, amenorrhea or polymenorrhoea), history of anovulation or ultrasonographic findings of polycystic ovarian morphology.

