### Aims and objectives

#### Primary:

1. To determine the prevalence of PCOS among women of reproductive age (a selected population (18 to 45)) in Trinidad.

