#### Secondary

2. To determine the distribution of phenotypes among women diagnosed with PCOS in the above objective overall and by ethnicity. PCOS sub phenotypes are as follows: Phenotype A – clinical and/or biochemical hyperandrogenism (HA) and oligi-/anovulation (OA), and polycystic ovarian morphology (PCOM); B – HA and OA; C – HA and PCOM; and D – OA and PCOM;
3. To determine the risks for, metabolic syndrome, depression, obstructive sleep apnea symptoms, fibroids, and general health issues for PCOS women versus women without PCOS in the age groups 18 – 45 years.
4. To determine the genotype of PCOS in Trinidad.

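### Inclusion criterion (b) admits only women who already show a PCOS feature, so the plan as written cannot give population prevalence, an unselected comparison group, or 495 women from 990 approached

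*Combined protocol and SAP*

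**What the plan says.** All references are to the combined protocol and SAP.

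- **Objective.** Under Aims and objectives, the primary aim is "To determine the prevalence of PCOS among women of reproductive age", with the age range 18 to 45 and the place Trinidad. Outcome measures and variables adds the prevalence of PCOS symptoms to the primary outcome.
- **Sampling unit.** Strategies for Sampling, Recruitment and Retention states: "Sampling units are defined as individual unselected women between the ages of 18 and 45 years, identified in the community". The sample size uses 13.4%, taken from general-population studies.
- **Entry.** The Inclusion criteria require, beyond sex and age, that "The participants must have at least one of the following two features". The first feature is a sign or complaint of clinical hyperandrogenism (unwanted hair, scalp hair loss, persistent acne). The second is a sign or complaint of ovulatory dysfunction, including irregular menses, "history of anovulation or ultrasonographic findings of polycystic ovarian morphology".
- **How entry is applied.** The sampling section says: "In each sampled house, females would be prescreened and those that satisfy our inclusion criteria would be selected". Sampling technique repeats that recruits are those who meet the selection criteria.
- **Comparison.** Secondary objective 3 compares "PCOS women versus women without PCOS". No separate recruitment of controls is described.
- **Losses.** The 50% response rate is made up of hormone or contraceptive use 15%, hysterectomy or ovariectomy 3%, pregnancy 2%, refusal 20% and drop-out 10%.

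**The concern.** A sample cannot be both unselected and required to carry a feature. The features in (b) largely coincide with the hyperandrogenism, ovulatory and ovarian-morphology components that define phenotypes A to D, so entry depends on the outcome being measured. Four things are at stake.

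1. **Primary estimate.** Women with no feature never enter the denominator. The result is the proportion with PCOS among feature-positive women.
2. **Symptom prevalence.** Having at least one listed feature becomes 100% by construction. The prevalence of each qualifying symptom is inflated.
3. **Objective 3.** Women without PCOS will exist in the sample, but all of them have a feature. If the features are themselves related to metabolic syndrome, depression or sleep symptoms, the odds ratios are distorted. The documents do not allow the direction or size to be worked out.
4. **Recruitment and precision.** The loss list covers other eligibility failures (surgery, pregnancy) but not absence of a feature.

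Some true cases would also be missed at the household prescreen, for example a woman with biochemical hyperandrogenism and polycystic ovaries that have never been scanned.

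**Working it through.** **Inputs from the plan** (Study population; Strategies for Sampling, Recruitment and Retention): Z = 1.96, P = 0.134, D = 0.03, five loss items, 990 approached.

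**Step 1: reproduce the plan's figures.** n = Z²P(1 − P)/D² = 1.96² × 0.134 × 0.866 / 0.03² = 495.3, which matches the stated 495. Losses: 15 + 3 + 2 + 20 + 10 = 50%. Approached: 495 / 0.50 = 990. Per zone: 990 / 8 = 123.75, stated as about 124. The arithmetic is sound, but for unselected women only. Because 990 × 0.50 = 495 exactly, nothing is left for a further filter.

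**Step 2: add criterion (b).** Let f be the share of otherwise eligible women with a qualifying feature. **The documents give no value for f**, so a range is shown. Assume for now that every PCOS case passes (b), which means f is at least 0.134.

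- Enrolled = 990 × 0.50 × f = 495f
- Proportion with PCOS among those enrolled, p = 0.134 / f
- Half-width = 1.96 × √(p(1 − p) / (495f))
- Non-cases = 495f − 495 × 0.134 = 495f − 66.3
- Approached to enrol 495 = 495 / (0.50 × f)

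| f (assumed) | Enrolled | p | Half-width | Non-cases | Approached for 495 |
|---|---|---|---|---|---|
| 0.25 | 124 | 53.6% | ±8.8 | 57 | 3,960 |
| 0.50 | 248 | 26.8% | ±5.5 | 181 | 1,980 |
| 0.80 | 396 | 16.8% | ±3.7 | 330 | 1,238 |
| 1.00 (no filter) | 495 | 13.4% | ±3.0 | 429 | 990 |

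The overstatement is 1/f: fourfold at 0.25, twofold at 0.50 and 1.25-fold at 0.80.

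**Step 3: would reaching 495 be enough?** No. With 495 feature-positive women the half-width is 1.96 × √(0.536 × 0.464 / 495) = ±4.4 points at f = 0.25, and 1.96 × √(0.268 × 0.732 / 495) = ±3.9 at f = 0.50. Restoring ±3 would take 1,062 and 838 women respectively, and the estimate would still be of the wrong quantity.

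**Step 4: relax the two assumptions.**
- *Missed cases.* If only a share s of cases passes the prescreen, p = s × 0.134 / f. The values of p in the table are therefore upper values for their f.
- *Losses multiplied instead of added.* 0.85 × 0.97 × 0.98 × 0.80 × 0.90 = 0.582, or 576 of 990. Then 495 is reached only if f is at least 495 / 576 = 0.86.

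**Step 5: look for a denominator elsewhere in the plan.** Data management and Statistical analysis specifies no prevalence denominator, weighting or two-phase estimator. The register of potential participants (Study procedure) holds name, age, height, weight, blood pressure and telephone number, with no PCOS features. It cannot supply the denominator afterwards.

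**The case against.** The strongest reply is that an unselected sample was meant and (b) is stray wording. The sampling section calls the women unselected. Table 1 separates tests for all subjects from tests for those with oligomenorrhea, hirsutism or polycystic ovaries. The diagnostic tree is referenced to a study whose title describes an unselected population. A related reply is that all women in randomly sampled houses are prescreened, so prevalence could be recovered as cases over eligible women prescreened.

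Both carry some weight. They show that population prevalence is not out of reach in principle and that the defect is an internal contradiction. Neither rescues the text. Field staff apply the eligibility criteria, and (b) is mandatory there. Table 1 is not decisive, because a woman could enter with acne or alopecia alone. A two-stage estimate would need the feature status of every prescreened woman and some evaluation of those who screen negative, and the plan provides for neither.

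The phrase in the primary objective about a selected population does not help either, since the selection it names is the age range.

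The objections about size stand in part. Criterion (b) has no severity threshold, so f could be well above 50%, and the two- to fourfold figure describes only part of the possible range. With multiplied losses, 495 is attainable if f is at least 0.86. These points change the size of the error and leave its direction unchanged.

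**Conclusion.** The concern holds, and it must be fixed before the plan is used. As written, the enrolled sample estimates PCOS among feature-positive women, objective 3 has no unselected comparison group, and on the plan's own additive loss budget any f below 1 leaves fewer than 495 from 990 approached.

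The size is illustrative because f is assumed. For f of 25% to 50%, the observed proportion is about 54% to 27% against 13.4%, with 124 to 248 women enrolled. At f = 80% it is 16.8% with 396 women. These figures take the plan's 13.4% as true and assume that every case passes the prescreen. No later analysis can repair the primary estimate, because women without a feature would never have been evaluated.

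**What to change.** 1. Delete inclusion criterion (b), so that every sampled woman aged 18 to 45 who meets no exclusion criterion is enrolled and evaluated. Use the listed features only to assign PCOS status and phenotype.
2. State the estimator in the analysis section: prevalence = PCOS cases / all evaluated sampled women, with its 95% confidence interval. State how users of hormonal contraception are counted: the sample size is for untreated women, but the exclusion criteria do not exclude users.
3. Define the comparison group for objective 3 as all evaluated women without PCOS.
4. Align the prescreen sentence in the sampling section, and reconcile its random house sampling with the consecutive recruitment under Sampling technique.

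With (b) removed, 495 and 990 stand. The expected yield is 495 × 0.134 ≈ 66 cases and 429 unselected non-cases.

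The cost is a protocol amendment with ethics review. Women without features will need the standard evaluation, including ultrasound and blood sampling, but the 495 evaluations were already planned for unselected women, so the total does not rise.

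If the sponsor prefers to keep a symptom screen, the plan must become an explicit two-phase design: record feature status for every prescreened woman, evaluate a random sample of screen-negatives, and specify a weighted estimator. That would need new sample-size work. If women have already been enrolled under (b), rewording does not repair those data. They should be reported as the proportion with PCOS among feature-positive women.
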